# 4.12 Describe the process that you will employ to ensure the subjects are fully informed about this research study.

\* Addressed below:

## This description must include the following elements:

- who from the research team will be involved in the consent process (both the discussion and documentation);
- person who will provide consent or permission;
- · information communicated; and
- any waiting period between informing the prospective participant about the study and obtaining consent

In addition, address the following if applicable based on your subject population:

- process for child assent and parental permission
  - o continued participation if a child subject turns 18 during participation
- process for obtaining proxy consent and assent for decisionally impaired subjects
  - o continued participation if subject regains capacity to consent

Most of our participants are likely to be identified via the "UPMC Multiple Sclerosis and Related Disorders Registry" or by screening individuals with MS upcoming clinic visits. A potential participant who is deemed eligible via these screening procedures may be contacted and then sent the consent form for review prior to the study visit if they are interested. Thus, the potential participant will be given substantial time (days to weeks) to review the consent form and have an opportunity to contact study staff with any questions prior to enrollment. Our study coordinator will again provide a detailed review of the study with special focus on the potential benefits and risks of the study, and all of the potential subject's questions should be answered at the time of the consenting. The subject will be reminded that participation is voluntary and that if s/he does not want to participate, then refusal will not impact subsequent care. If the subject is still interested in participating,

then one of the investigators (PI/Co-PI) will obtain informed consent and sign the Certification of Informed Consent. A copy of the consent form will be given to the subject.

# 4.13 Are you requesting an exception to either IRB policy related to the informed consent process?

- For studies involving a drug, device or surgical procedures, a licensed physician who is a listed investigator is required to obtain the written informed consent unless an exception to this policy has been approved by the IRB
- For all other studies, a listed investigator is required to obtain consent (Note: In order to request an exception to this policy, the study must be minimal risk)
- \* No

If **Yes**, provide a justification and describe the qualifications of the individual who will obtain consent:

# 4.14 Will you inform research subjects about the outcome of this research study following its completion?

\* Yes

If **Yes**, describe the process to inform subjects of the results:

Patients and the PI/Co-PI will be debriefed after Phase 3 by the study coordinator. They will then be seen by the PI/Co-PI in a standard follow up clinic visit. The debriefing is a necessary part of the patient's continuity of care, as it may direct changes in patient management (i.e. if a patient did not have a clinical improvement in the placebo arm, they may be offered study medication or its equivalent). As a patient reported outcome is the primary outcome measure, the "results" of the study should be self-evident to patients.

Section: Section 5 - Potential Risks and Benefits

[reviewer notes-]

5.1 Describe potential risks (physical, psychological, social, legal, economic or other) associated with screening procedures, research interventions/interactions, and follow-up/monitoring procedures performed specifically for this study:

\*

	Research Activity:	Bowel Diary
	Common Risks:	No Value Entered
View	Infrequent Risks:	All efforts will be made to keep the information secure. However, there is a small chance of a breach in confidentiality with any medical record keeping.
	Other Risks:	No Value Entered
	Research Activity:	Medical Record Review
	Common Risks:	No Value Entered
View	Infrequent Risks:	There is a small chance of a breach in confidentiality with any medical record review, either by Care Team staff as a part of routine care, or by the study coordinator in the process of

		accessing information from the "UPMC Multiple Sclerosis and Related Disorders Registry" (PRO12010609).
	Other Risks:	No Value Entered
	Research Activity:	Research Intervention
View	Common Risks:	The study medication, bisacodyl 10 mg rectal suppository, is available over-the-counter for routine use for constipation. Side effects of bisacodyl rectal suppositories include stomach discomfort, nausea, faintness, rectal burning, mild cramps, and diarrhea but these are potential issues are uncommon. There are no side effects to taking placebo, but patients could have a risk of continued bowel dysfunction if they do not receive the study drug.
	Infrequent Risks:	No Value Entered
	Other Risks:	No Value Entered
	Research Activity:	Screening and Enrollment
View	Common Risks:	Minimal risk of patient's concern that participation is expected or that their care would be impacted by opting out.
	Infrequent Risks:	No Value Entered
	Other Risks:	No Value Entered
	Research Activity:	Study Survey Data
	Common Risks:	No Value Entered
View	Infrequent Risks:	All efforts will be made to keep the information secure. However, there is a small chance of a breach in confidentiality with any medical record keeping.
	Other Risks:	No Value Entered
	1	

# 5.1.1 Describe the steps that will be taken to prevent or to minimize the severity of the potential risks:

The study coordinator will contact patients to make sure that they are not having any problems during the study period. Patients will be encouraged to contact study staff regarding any concerns during the study period at any time.

Our study coordinator will emphasize that participation is completely voluntary, that patients can always opt out even once enrolled, and that their decision to participate or not will have no impact on care decisions.

# 5.2 What steps will be taken in the event that a clinically significant, unexpected disease or condition is identified during the conduct of the study?

### \* Not Applicable

**5.3** All the risk questions (screening, intervention/interaction, follow-up) have been merged into one question (5.1).

Do any of the research procedures pose a physical or clinically significant psychological risk to women who are or may be pregnant or to a fetus?

\* No

[reviewer notes¬]

- 5.5 Do any of the research procedures pose a potential risk of causing genetic mutations that could lead to birth defects?
  - \* No

[reviewer notes¬]

- Are there any alternative procedures or courses of treatment which may be of benefit to the subject if they choose not to participate in this study?
  - \* No

If **Yes**, describe in detail:

[reviewer notes¬]

- 5.7 Describe the specific endpoints (e.g., adverse reactions/events, failure to demonstrate effectiveness, disease progression) or other circumstances (e.g., subject's failure to follow study procedures) that will result in discontinuing a subject's participation?
  - \* Not applicable There are no anticipated circumstances that would lead to discontinuing a subject's participation in this research study.

[reviewer notes-]

- 5.8 Will any individuals other than the investigators/research staff involved in the conduct of this research study and authorized representatives of the University Research Conduct and Compliance Office (RCCO) be permitted access to research data/documents (including medical record information) associated with the conduct of this research study?
  - \* No
- 5.9 Has or will a Federal Certificate of Confidentiality be obtained for this research study?
  - \* No
- 5.10 Question has been moved to 5.17
- 5.11 Question has been moved to 5.16

[reviewer notes¬]

# 5.12 Does participation in this research study offer the potential for direct benefit to the research subjects?

Yes - Describe the direct benefit that subjects may receive as a result of study participation. Indicate if all, or only certain, of the subjects may derive this potential benefit.

#### Describe the benefit:

Most patients are likely to see some subjective improvement in bowel function (even those in the placebo arm), since all patients will be will be recommended to use some intervention to alter stool form (i.e. laxatives or anti-diarrheals). The study participants assigned to the active medication arm may derive subjectively greater improvement in bowel related symptoms (the primary hypothesis).

5.13 Describe the data and safety monitoring plan associated with this study. If the research study involves multiple sites, the plan must address both a local and central review process.

The Principal Investigator, [name], will meet with [name] (Co-PI) every 8 weeks to evaluate the progress of the research study, including assessment of data quality and subject recruitment.

Data and Safety will be further monitored by a joint meeting every 6 months between the PI, Co-PI, and [name], a nurse manager of the UPMC MS Clinic who oversees clinical trials for the group. This group will be responsible for the following: 1) reviewing the data accumulated from the ongoing study; 2) advising the principal investigator or study sponsor of necessary changes to elements of the study that affect subject safety; 3) determining whether there has been any change to the risk-to-benefit assessment during the course of the study; and 4) determining whether the study should continue as designed. They will also review, on an ad hoc basis, any serious adverse events (SAE) that are directly related to the study medication as given according the study protocol. The results of the DSMB meetings will be submitted to the IRB at the time of the annual renewal.

[reviewer notes¬]

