During Phase 2, patients will meet the PI / Co-PI in the UPMC Digestive Disorders Center (DDC) for anorectal function testing (anorectal sensory and High Resolution Anorectal Manometry (HRAM) testing), which typically takes about 45 minutes. This is a one time, routine test that is performed in patients with anorectal dysfunction. It involves the transanal placement of a thin manometry catheter with inflatable balloon into the rectum. The patients' threshold to first sensation of rectal filling, urgency, and pain, basal anal resting pressure, voluntary anal squeeze pressure, and the rectal-anal inhibitory reflex (RAIR) to rectal distention and during simulated strain, as well as the ability to evacuate a 50 cc volume rectal balloon within one minute are all recorded variables and constitute normal components of such testing. The PI/Co-PI will meet with patients in the DDC GI lab around the time of the anorectal testing, and based on the clinical assessment of dominant bowel symptoms, provide patients with guidance on baseline interventions (either laxative or anti-diarrheal use). For example, the use of oral therapies is predicated on patients' typical stool form (using the Bristol Stool Scale 1-7) - the goal is to achieve a typical bowel movement of a 3-5 in consistency. Patients with Bristol 1-2 stools (hard) will use 8.5 - 42 grams of PEG-3350 laxative per day, while those with Bristol 6-7 (loose) will use 0.5 - 4 grams of loperamide per day, titrated to the goal. At the end of Phase 2 visit, patients will be given instructions on study medication use and will obtain the study drug (double-blinded; study drug "blister" packets would have been previously randomized by the pharmacy and delivered to the DDC). Patients will be encouraged to continue daily bowel diaries for the ensuing 4 weeks of the study trial period. Phase 2, including the physiological testing assessment and meeting with the PI/Co-PI, should take about 1.5 hours in total.

During the next 4 weeks, patients will use recommended oral therapies in addition to the every other day use of the rectal suppository study medication. They will record events in their daily bowel diary.

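### Section 5.13 limits ad hoc SAE review to events already judged drug-related under per-protocol use, and the general six-monthly review has no planned adverse event data behind it

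*Combined protocol and SAP*

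**What the plan says.** Section 5.13 sets up two layers of review by the PI, the Co-PI and a clinic nurse manager.

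- **Scheduled.** The group meets every six months. Its duties include "reviewing the data accumulated from the ongoing study" and "determining whether there has been any change to the risk-to-benefit assessment during the course of the study". None of the scheduled duties is limited by relatedness, adherence or drug.
- **Ad hoc.** The next sentence opens "They will also review, on an ad hoc basis" and then gives the scope: "any serious adverse events (SAE) that are directly related to the study medication as given according the study protocol". This is the only rule in the plan that is specific to SAEs.

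On contact with patients, 5.1.1 says: "The study coordinator will contact patients to make sure that they are not having any problems during the study period". Section 2.6 describes the coordinator's contact during the trial period as a check on compliance.

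On treatment, 2.6 says that "patients will use recommended oral therapies in addition to the every other day use of the rectal suppository study medication". The oral agents are PEG-3350 or loperamide, chosen by stool form, and they are used in both arms. In that sentence the term study medication means the suppository.

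The study is classed as above minimal risk (T3.0).

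**The concern.** The ad hoc rule asks for two judgements before an SAE is taken up: that the drug caused it, and that the drug was used as the protocol directs. The plan does not say who makes these judgements or by what criteria. In a randomized, placebo-controlled trial, the evidence on harm that depends least on such case-by-case calls is the count of all events in each arm. A rule that starts from attribution puts that evidence second, and here no other part of the plan supplies it.

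At stake is whether the group can do what 5.13 asks of it. It must reassess risk against benefit, and the benefit side is measured in detail while the risk side has no planned record of its own.

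**Working it through.** The concern rests on reading sections against each other. Arithmetic enters only at steps 5 and 6.

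1. **What the ad hoc trigger leaves out.** The scope has two conditions (directly related; given per protocol) and one object (the study medication). Three classes of SAE fail at least one of these: those judged unrelated, those after off-schedule suppository use, and those attributed to PEG-3350 or loperamide. The third class depends on study medication meaning the suppository, as in 2.6.

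2. **What the scheduled review could see.** In principle it could see all three classes, because its duties are unrestricted. In practice it can see only what is recorded.

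3. **What is recorded.**
   - Study measures (2.6): nine items, none of them adverse events.
   - Endpoints (2.17): one primary and eight secondary, none of them adverse events.
   - Analyses (2.18): Fisher's exact test, t-tests and logistic regression, with adverse events not named.
   - Coordinator contact (2.6, 5.1.1): no form, grading or record is described.
   - Other routes: 2.7 plans no research follow-up procedures, and 5.2 and 5.7 are answered as not applicable.

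4. **Partial capture by the diary.** Section 5.1 names six side effects of the suppository: diarrhea, cramps, nausea, faintness, rectal burning and stomach discomfort. The diary holds stool form, number of bowel movements and incontinence episodes, so it bears on one of the six. The symptom and quality-of-life questionnaires are planned as outcome measures, and their items are not in the text available. Section 5.1 lists no side effects of the oral agents.

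5. **Timing.** An SAE outside the trigger has its first stated safety review at the next joint meeting, up to six months away. Treatment lasts four weeks and participation up to eight (2.11). The PI and Co-PI also meet every eight weeks, but the stated purpose is progress, including data quality and recruitment.

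6. **How many events to expect, and what a by-arm table can show.** The plan's sample size reproduces: 2 × (1.960 + 0.842)² × 4² / 3² = 27.9, so 28 per arm and 56 in total; 56 / (1 − 0.20) = 70 enrolled, or 35 per arm at 1:1. The plan gives no SAE rate, so the rates below are assumptions.

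| Assumed SAE rate per patient | Expected in 70 | Chance of at least one in an arm, 1 − (1 − p)^35 |
|---|---|---|
| 1% | 0.7 | 30% |
| 2% | 1.4 | 51% |
| 5% | 3.5 | 83% |

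By two-sided Fisher's exact test with 35 per arm, 5 events against 0 gives p = 0.054 and 6 against 0 gives p = 0.025. A by-arm table should therefore be descriptive. The first of these results also shows that reading every SAE adds little work.

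**The case against.** The strongest reply is that the ad hoc sentence adds to the standing duties and does not replace them. This stands. A reader might infer from 5.13 that only drug-related SAEs are covered and that the rest are never reviewed. The text does not support that, because the six-monthly duties are unrestricted.

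A second reply is that the PI and Co-PI are two of the group's three members. They guide the oral therapy and see patients at Phases 2 and 3, so an event known to them is known to the group whatever its label. This stands in part. Knowing of an event is not the same as recording it or reviewing it under a stated rule. The PI and Co-PI also learn each patient's arm once the Phase 3 questionnaires are done, so a judgement of relatedness made after that point can depend on known allocation.

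A third reply is that the diary lets diarrhea be compared by arm with the tests in 2.18, and that the coordinator asks about problems. Both are true, and both are partial (steps 3 and 4).

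A reader might also infer that the ad hoc rule is what prevents a comparison between arms. It is not. That gap comes from the absence of adverse events among the measures, endpoints and analyses.

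Two figures are tempting as measures of size, and neither is one. Zero events in 35 patients leaves a one-sided 95% upper bound of 1 − 0.05^(1/35) = 8.2%, but that follows from the sample size and would be the same with unrestricted review. Each patient receives 20 suppositories for 28 / 2 = 14 scheduled doses, which leaves 6 spare. The spares are supplied to assess compliance and unused ones are collected, so they show that off-schedule use is possible, not that it is expected.

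Finally, the product is sold over the counter, is given for four weeks and is declared to be within its labeling. That argues for a modest grade, not for leaving harms unrecorded.

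**Conclusion.** The concern holds in this form: ad hoc SAE review is limited to events already judged directly related to per-protocol study medication; the six-monthly review is general, but it has no planned adverse event data beyond the diary; and no by-arm comparison of harms is planned.

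Its size is three classes of SAE outside the trigger, a possible wait of up to six months for those events, and five of the six named side effects with no diary item. The number of events affected cannot be calculated from the plan. Sample size and the primary analysis are untouched. This is an inexpensive improvement that should be made, not a flaw that undermines the trial.

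The conclusion rests on two assumptions. Study medication in 5.13 means the suppository. The uploaded attachments and the consent form, which were not available for this review, do not set out adverse event procedures; if they do, 2.6 and 5.13 should refer to them.

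**What to change.** 1. In 5.13, have the group review every SAE, regardless of judged relatedness or adherence. Relatedness can still be recorded, but it should not decide what is reviewed.
2. In 2.6, add adverse events to the study measures, including events on the oral agents. Ask about them at the coordinator's already planned contacts and at Phase 3, together with the exit questionnaires and so before the arm is revealed. State how seriousness and relatedness are defined and who judges them.
3. In 2.18, add a descriptive table of adverse events and SAEs by randomized arm at the end of the trial, with no formal test.

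The cost is a short adverse event record, which has to be created because the plan describes no contact form, with brief definitions, and a few more events to read (about 0.7 to 3.5 SAEs in 70 patients under the assumed rates of 1% to 5%). No new visit and no change in sample size is needed.

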# **Section 5 - Potential Risks and Benefits of Study Participation**

**5.14 What precautions will be used to ensure subject privacy is respected?** (e.g. the research intervention will be conducted in a private room; the collection of sensitive information about subjects is limited to the amount necessary to achieve the aims of the research, so that no unneeded sensitive information is being collected, drapes or other barriers will be used for subjects who are required to disrobe)

The interactions between patients and the study coordinator/study staff (informed consent, study questionnaires) will be conducted in a private room, likely within the MS Clinic on initial study entry and in the DDC at study close.

Enrolled patients undergoing anorectal manometry testing will have the testing performed in a private room in the DDC GI Lab, adjacent to a private bathroom / changing area.

**5.15** What precautions will be used to maintain the confidentiality of identifiable information? (e.g., paper-based records will be kept in a secure location and only be accessible to personnel involved in the study, computer-based files will only be made available to personnel involved in the study through the use of access privileges and passwords, prior to

Section: Section 5 - Potential Risks and Benefits

access to any study-related information, personnel will be required to sign statements agreeing to protect the security and confidentiality of identifiable information, whenever feasible, identifiers will be removed from study-related information, precautions are in place to ensure the data is secure by using passwords and encryption, because the research involves web-based surveys, audio and/or video recordings of subjects will be transcribed and then destroyed to eliminate audible identification of subjects)

All paper-based records (informed consent forms, study questionnaires and daily bowel diaries) will be kept in a secure location and only be accessible to personnel involved in the conduct and analysis of the study.

Electronic files used in the analysis will contain only de-identified data.

5.16 If the subject withdraws from the study, describe what, if anything, will happen to the subject's research data or biological specimens.

If the subject withdraws from the study after having passed Phase 1 (i.e. baseline measures of bowel dysfunction and quality of life), we would keep the data for an "intention-to-treat" analysis (with the assumption of an non-response). If a subject has not completed Phase 1, then the research data will be destroyed.

**5.17** Following the required data retention period, describe the procedures utilized to protect subject confidentiality. (e.g., destruction of research records; removal of identifiers; destruction of linkage code information; secured long-term retention)

We will destroy primary research records with any identifiers, but may opt to retain deidentified electronic data on a secured server for future re-analysis. Per University of Pittsburgh guidelines, research records will be archived for a minimum of seven years after final reporting or publication of a project.

Section: Section 6 - Costs and Payments

[reviewer notes-]

6.1 Will research subjects or their insurance providers be charged for any of the procedures (e.g., screening procedures, research procedures, follow-up procedures) performed for the purpose of this research study?

Yes; charges will be billed only for procedures performed as part of the subject's routine clinical care as addressed in question 2.9

[reviewer notes-]

6.2 Will subjects be compensated in any way for their participation in this research study?

\* No

